 - Patients in Group 1 who are randomized to Arm B (SoC) and experience first relapse (MRD⁺ or frank relapse) post-HSCT or experience relapse prior to randomization
 - Patients with frank relapse will enter into Subgroup C while patients with MRD+ disease will enter into Subgroup D
 - Sa fety Lead-in (Cohorts I and II) and Cohorts III-V defined as patients whose prior treatment course does not meet precise eligibility criteria but may still be approved upon review by the Sponsor as described above for Group 2 only

Note: Engra ftment must be confirmed post-transplant (absolute neutrophil count >1000/m³ without granulocyte colony-stimulating factor for 7 days, donor chimerism >50%).

- 1. Are \geq 18 years of a ge prior to a dministration of MT-401
- 2. Patients must have donor-derived cells a vailable to make MT-401
- 3. Karnofsky/Lansky score of ≥60
- 4. Life expectancy≥12 weeks
- 5. Adequate blood, liver, and renal function
 - Blood: Hemoglobin \geq 7.0 g/dL (can be transfused)
 - Liver: Bilirubin ≤1.5X upper limit of normal; a spartate aminotransferase ≤3X upper limit of normal
 - Renal: Serum creatinine \leq 2X upper limit of normal or measured or calculated creatinine clearance \geq 45mL/min
- 6. Sexually active patients must be willing to utilize one of the highly effective birth control methods or practice complete a betinence starting from Screening for T cell infusion until 6 months a fter the last T cell infusion. Male patients who are sexually active must a gree to use a condom during this period.
- 7. Patients are allowed to be on experimental conditioning regimens prior to transplant if no planned maintenance therapy post-transplant.
- 8. In Group 2, patients may receive bridging thempy at the investigators' discretion in situations where MT-401 is not ready for a dministration or the treating physician

Confidential Page 13 of 74

believes the patient would benefit (particularly in cases of high tumor burden) for ≤6 months as long as the following criteria are met:

- Disease assessment including bone marrow biopsy to be performed within 14 days prior to a dministration of MT-401 (patients may receive MT-401 even if CR is a chieved post-bridging therapy but will be a nalyzed separately; additionally, patients must have ≤30% bone marrow blasts)
- At least 4 half-lives or 1 week has passed after administration of bridging therapy whichever is shorter

Patient Exclusion Criteria:

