1.2. Study Schematic

Figure 1 Study Schematic

Abbreviations: CR=complete remission; HSCT=hematopoietic stem cell transplant; SoC=standard of care

- ^a Safety Lead-in (Cohorts I and II) and Cohorts III-V defined as patients who fit a majority of the criteria for Group 2 only (as determined by the Sponsor).
- *Patients in Groups 1 and 2 will receive 100 x 10⁶ cells, but the Sponsor may change the Phase 2 dose regimen to either a higher dose (Cohort III) and/or to the product manufactured using the accelerated process (Cohorts IV and V).

Notes:

- Disease assessment and group assignment occur at Day 80 post-HSCT (±5 days) for Group 1 patients.
- Patients in Group 1 Arm B who relapse after randomization may cross over to Group 2 to receive MT-401 if the particular subgroup is open and/or Sponsor agreement.
- Patients may be identified post-HSCT and enter Group 2 if the same donor cell is available to provide cells for manufacturing MT-401 and eligibility is fulfilled.
- If relapse occurs less than 80 days post-HSCT and T cells have been manufactured and stored, the patient may receive MT-401 and be included in a subgroup analysis of Group 2.
- Group 2 patients may receive MT-401 even if CR_{MRD} is achieved post-bridging therapy but will be analyzed separately.

Confidential Page 17 of 74

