3. OBJECTIVES AND ENDPOINTS

Table 3: Objectives and Endpoints

Phase	Objectives	Endpoint
	Primary	
Sa fety Lead-in (Cohort I and II) & Cohorts III-V	 To assess sa fety and tolerability of MT-401: Manufactured using peptides produced by two different vendors (Safety Lead-in: Cohorts I and II). At a higher dose than the dose used in the Phase 2 portion of the study (Cohort III). Manufactured using an accelerated manufacturing process at two dose levels (Cohort IV and V) 	DLTs Sa fety (including but not limited to): TEAEs, SAEs, deaths and clinical laboratory abnormalities per National Cancer Institute (NCI) Common Terminology Criteria for Adverse Events (CTCAE, Version 5.0)
Phase 2 - Adjuvant (Group 1)	To compare relapse-free survival (RFS) for MT-401 (Arm A) vs standard of care (SoC; Arm B)	RFS

Confidential Page 26 of 74

Phase	Objectives	Endpoint
Phase 2 – Active Disease (Group 2):	 Subgroup C (frank relapse): to estimate complete remission (CR) rate and duration of CR (DOCR) Subgroup D (MRD⁺): to estimate complete remission (CR_{MRD}-) rate and duration of CR without minimal residual disease (DOCR_{MRD}-) 	 Subgroup C: CR rate DOCR Subgroup D: CR_{MRD}-rate DOCR_{MRD}-
	Secondary (Efficacy)	
Sa fety Lead-in (Cohorts I and II) & Cohorts III-V	 To assess efficacy of MT-401: Manufactured using peptides produced by two different vendors (Safety Lead-in: Cohorts I and II). At a higher dose than the dose used in the Phase 2 portion of the study (Cohort III). Manufactured using an accelerated manufacturing process at two dose levels (Cohort IV and V) 	CR rate and DOCR (Active disease patients)
Phase 2 (Adjuvant-Group 1)	 To analyze overall survival (OS) for MT-401 (Arm A) and SoC (Arm B) To compare graft-versus-host disease RFS (GRFS) for MT-401 (Arm A) vs SoC (Arm B) 	• OS • GRFS
Phase 2 (Active Disease- Group 2: Subgroups C and D)	 To evaluate overall response rate (ORR), duration of response (DOR), progression-free survival (PFS) and OS for MT-401 alone To evaluate RFS, OS, and GRFS for patients who achieve CR following bridging therapy 	ORRDORPFSOSRFSGRFS
	Secondary (Safety)	
Phase 2 (Adjuvant-Group 1 and Active Disease- Group 2)	To evaluate the safety and tolerability of administering donor-derived MT-401 to patients with AML post-HSCT	 GVHD Assessments Vital signs Clinical laboratory assessments Physical examination AEs
	Exploratory	

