 - Blood: Hemoglobin \geq 7.0 g/dL (can be transfused)
 - Liver: Bilirubin ≤1.5X upper limit of normal; aspartate aminotransferase ≤3X upper limit of normal
 - Renal: Serum creatinine ≤2X upper limit of normal or measured or calculated creatinine clearance >45mL/min
- 7. Sexually active patients must be willing to utilize one of the highly effective birth control methods or practice complete abstinence starting from Screening for T cell infusion until 6 months after the last T cell infusion (see details in Section 8.3.5). Male patients who are sexually active must agree to use a condom during this period.
- 8. Patients are allowed to be on experimental conditioning regimens prior to transplant if no planned maintenance therapy post-transplant.
- 9. In Group 2, patients may receive bridging therapy at the investigators' discretion in situations where MT-401 is not ready for administration or the treating physician believes the patient would benefit (particularly in cases of high tumor burden) for ≤6 months as long as the following criteria are met:
 - Disease assessment including bone marrow biopsy to be performed within 14 days prior to administration of MT-401 (patients may receive MT-401 even if CR MRD is achieved post-bridging therapy but will be analyzed separately; additionally, patients must have ≤30% bone marrow blasts)
 - At least 4 half-lives or 1 week has passed after administration of bridging therapy whichever is shorter

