9.1.2. Active Disease and Late Relapse Population (Group 2)

A total of approximately 60 Group 2 patients are planned to be enrolled and treated with MT-401, 30 patients in Subgroup C (frank relapse patients) and 30 patients in Subgroup D (MRD $^+$). After approximately the first 10 patients in each subgroup have progressed or have had the opportunity to be followed for 6 months, clinical safety and efficacy will be reviewed comprehensively. Patients who develop CR_{MRD} after bridging therapy and patients who relapse early (defined < 90 days \pm 10 days post-transplant and termed Group 2 Early Relapse patients) will be analyzed separately, and not be counted as part of the 60 patients in Group 2.

Overall response rates in the literature vary widely and range from 10% to 60% (Loren and Porter, 2008; Porter et al, 2010). Complete remission rates would be expected to be lower than ORR rates. The sample size of 30 per subgroup is not based on a formal power calculation. An increase in the CR rate of greater than 10-15% compared to historical rates for standard of care would be considered clinically meaningful.

If the decision is made to dose patients in Phase 2 with any of the MT-401 dosing regimens evaluated in Cohorts III-V, enrollment will continue in Phase 2 Group 2 to achieve 60 evaluable patients treated with the final MT-401 dose and manufacturing process, thereby replacing any patients that have not been treated with the final Phase 2 product as determined by the Sponsor.

For historical control response rates ranging from 5% to 40%, the observed treatment effects (and associated 95% confidence intervals) needed to attain 80% and 90% power with a sample size of 30 patients per subgroup are provided in Table 7.

Confidential Page 50 of 74

Table 7. Power^a and 95% Confidence Intervals Relative to Historical Control Rates

Historical Control CR Rate	Observed Treatment Effect (80% Power) (95% CI)	Observed Treatment Effect (90% Power) (95% CI)
5%	21% (9%, 40%)	25% (11%, 44%)
10%	29% (14%, 48%)	32% (17%, 52%)
15%	36% (19%, 55%)	40% (22%, 59%)
20%	43% (25%, 62%)	47% (28%, 66%)
25%	50% (31%, 68%)	53% (34%, 72%)
30%	53% (34%, 71%)	57% (37%, 75%)
35%	60% (40%, 77%)	63% (44%, 80%)
40%	63% (43%, 79%)	66% (47%, 82%)

^a based on a 1-sided exact test at the 0.05 alpha level.

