assessments	assessment prior to the missed disease	
	assessments	

Abbreviations: AML=acute myeloid leukemia; RFS=relapse-free survival

RFS curves will be estimated using the Kaplan-Meier (KM) product limit method. For Group 1, the hazard ratio and corresponding 95% confidence interval (CI) will be estimated using a Cox proportional hazards model using randomized arm and two stratification factors as covariates. The KM estimate of the medians will be reported, and the corresponding 95% CI will be computed. KM estimates of RFS rates at milestone time points will be reported along with two-sided 95% CIs using Greenwood's formula, provided the minimum follow-up in patients exceeds the time point to support stable estimation of the rate. In addition to the Cox model, a stratified log-rank test will be used to compare the treatment arms, stratified by pre-transplant MRD status (MRD+ vs. MRD-/Unknown) and cytogenetic risk (Unfavorable vs. Other).

RFS is defined as the time between the date of first dose and the date of first relapse per ELN recommendations or death by any cause for Group 2 patients, and will be summarized for Group 2 Subgroup D patients and those in Group 2 who are in CR_{MRD} prior to administration of MT-401.

9.3.3. Primary Efficacy Analysis: Group 2

The primary endpoints for Group 2 are CR rate and duration of complete response. For Group 2 Subgroup C, CR rate is defined as the proportion of treated patients who achieve a best response of CR_{MRD} - or CR using the ELN recommendations. For Group 2 Subgroup D, CR rate is defined as the proportion of treated patients who achieve a best response of CR_{MRD} -. Best overall response (BOR) is defined as the best response designation recorded between the date of first dose and the date of objectively documented progression or relapse per ELN recommendations or the date of subsequent therapy, whichever occurs first. For patients without documented progression or subsequent therapy, all available response designations will contribute to the BOR assessment.

The primary analysis will occur after all patients treated have been followed for 6 months.

For Group 2 Subgroup C, duration of complete response is defined as the time between the date of first documented response of CR_{MRD}- or CR to the date of the first documented relapse per ELN recommendations or death due to any cause, whichever occurs first. For Group 2 Subgroup D, duration of

Confidential Page 53 of 74

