9.3.4. Secondary Analyses

9.3.4.1. Overall Survival (Groups 1 and 2)

Overall survival is defined as the time from randomization (Group 1) or first dose (Group 2) to the date of death. A patient who has not died will be censored on their last contact date ("last known alive date").

The statistical methods for analyzing OS are identical to those described for RFS.

Patients in Group 2 who achieve CR_{MRD}. post-bridging therapy will be summarized separately for OS.

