7.6 Determination of Sample Size

Approximately 6-12 patients are expected to be enrolled in the Safety Lead-in portion of this study per a standard 3+3 design with 2 planned cohorts. In addition, approximately 9-18 patients (3-6 patients per cohort) are expected to be treated in the Cohorts III-V portion of this study as per a standard 3+3 design.

A total of 150 Group 1 patients will be randomized with a 1:1 allocation to receive MT-401 or to be under observation (SOC arm). Median RFS for the SOC arm is expected to be approximately 8 months. A clinically meaningful increase in median RFS for the MT-401 arm over SOC is thought to be 2 months or more. The primary analysis will be conducted when 90 RFS events have been observed. Ninety (90) RFS events provides 80% power with alpha=0.05 (two-sided) to detect a median RFS improvement of 6.5 months over the assumed SOC median RFS of 8 months (hazard ratio=0.55). Ninety RFS will be observed assuming uniform accrual of 150 patients (75 per arm) over a 50-month period and an additional 12 month minimum follow-up period. The DMC and Sponsor will review data from Phase 2 based on the planned interim analyses described in [Section 7.4.7.3](#).

If the decision is made to dose patients in Phase 2 with any of the MT-401 dosing regimens evaluated in Cohorts III-V, enrollment will continue in Phase 2 Group 1 to achieve 150 evaluable patients randomized and approximately 75 patients treated with the final MT-401 dose and the intended manufacturing process, thereby replacing any patients that have not been treated with the final Phase 2 product, as determined by the Sponsor.

A total of approximately 60 Group 2 patients are planned to be enrolled and treated with MT-401, 30 patients in Subgroup C (frank relapse patients) and 30 patients in Subgroup D (MRD⁺). After approximately 10 patients in each subgroup have progressed or had the opportunity to be followed for 6 months, clinical safety and efficacy will be reviewed comprehensively. Patients who develop CR_{MRD-} after bridging therapy and patients who relapse early (defined as less than 90 days ± 10 days and termed Group 2 Early Relapse patients) will be analyzed separately, and not be counted as part of the 60 patients in Group 2.

The sample size of 30 per subgroup is not based on a formal power calculation. An increase in the CR rate of greater than 10-15% compared to historical rates for standard of care would be considered clinically meaningful.

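### The plan does not say when Subgroup C or D is fixed and sets aside only post-bridging CRMRD-, so a CR present before first dose can count as a Subgroup C primary response

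*Protocol*

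**What the plan says.** **Who is set aside after bridging.** The extracted text often drops the minus sign, so I read CR MRD in these places as CRMRD-.

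- Protocol 5.1: "patients may receive MT-401 even if CR MRD is achieved post-bridging therapy but will be analyzed separately".
- Protocol 1.2, notes to Figure 1: "Group 2 patients may receive MT-401 even if CR_{MRD} is achieved post-bridging therapy", again with separate analysis.
- Protocol 9.1.2 and SAP 7.6, the only places that say who is not counted in the 60: "Patients who develop CR_{MRD} after bridging therapy and patients who relapse early" and "Patients who develop CR_{MRD-} after bridging therapy and patients who relapse early".
- Protocol 1.1 Synopsis, same criterion as 5.1: "patients may receive MT-401 even if CR is a chieved post-bridging therapy", with no MRD qualifier.

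**Secondary post-bridging summaries.** Protocol 9.3.2 summarizes RFS for Subgroup D and for "those in Group 2 who are in CR_{MRD} prior to administration of MT-401". Protocol 9.3.4.1 says that the patients in CRMRD- "post-bridging therapy will be summarized separately for OS". Protocol Table 3 instead has "To evaluate RFS, OS, and GRFS for patients who achieve CR following bridging therapy", and SAP 5.2, 6.4.1.3 and 7.4.5 also use plain CR. SAP 7.7 reports no changes from the protocol.

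**Subgroup.** Protocol 4.1 and 5.1 and SAP 6.1 send frank relapse to C and MRD-positive disease to D, without naming the assessment that decides. Protocol 4.4 enrolls Group 2 patients before manufacturing starts, and bridging may last up to 6 months. For crossover patients the Schedule of Activities puts Baseline after bridging, but does not tie it to subgroup.

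**Response.** Protocol 9.3.3 and SAP 6.4.1.2 count CRMRD- or CR as a response in C, and only CRMRD- in D. Best response is taken from first dose onward. Protocol Table 6 notes that CR may be MRD-positive or MRD-unknown.

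**The concern.** CR rate and duration of CR are the primary endpoints of Subgroup C, a single open-label arm of 30 read against historical rates. Bridging chemotherapy can itself produce a CR. A patient in CRMRD- after bridging is set aside. A patient in CR with MRD positive or unknown is not set aside under the wording of 5.1, 9.1.2 and SAP 7.6, and no rule requires CR to be absent before first dose. If that patient is still in Subgroup C and still in CR after dosing, a chemotherapy remission is credited to MT-401. If the rule stays open, it will be settled when responses are already known.

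**Working it through.** **Step 1. Follow one patient through the rules.** Take a patient who enters with frank relapse and is in CR after bridging, before first dose.

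| Status before first dose | Subgroup fixed at relapse | Subgroup reset after bridging |
|---|---|---|
| CRMRD- | Set aside | Set aside |
| CR, MRD-positive | Stays in C; counts if CR is recorded after dosing | Fits D by the MRD-positive definition in Protocol 4.1; CR alone is not a response there |
| CR, MRD unknown | Stays in C; counts if CR is recorded after dosing | No stated place |

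If the synopsis wording (any CR) governed the primary count, all three rows would be set aside.

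**Step 2. Reproduce the plan's own figure.** Inputs from Protocol 9.1.2 and Table 7: n = 30 and a one-sided exact test at 0.05. The cut r is the smallest count with P(X ≥ r | 30, p0) ≤ 0.05.

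- p0 = 10%: P(X ≥ 6) = 0.073 and P(X ≥ 7) = 0.0258, so r = 7. Power is 0.810 at the tabulated 29% and 0.890 at 32%.
- p0 = 20%: P(X ≥ 10) = 0.061 and P(X ≥ 11) = 0.0256, so r = 11. Power is 0.811 at 43% and 0.907 at 47%.

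Over the whole table, 15 of 16 entries reproduce within 2 power points. The other (historical 35%, 80% power) gives 82.5%, a rounding matter.

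SAP 7.4.7.5 tests Group 2 CR at two-sided 0.05. With 0.025 in the upper tail the cuts are 8/30 (tail 0.0078) and 12/30 (tail 0.0095).

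**Step 3. Add pre-dose CRs, with no drug effect.** The number of such patients is my assumption. If k of the 30 are already in CR and all remain so, the chance of reaching the cut is P(k + Bin(30 − k, p0) ≥ r).

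For k = 1, p0 = 10% and r = 7, this is P(Bin(29, 0.10) ≥ 6) = 0.0637.

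If three patients each have a 50% chance of still being in CR after dosing, and count as non-responders otherwise, the chance is the sum over j = 0 to 3 of P(Bin(3, 0.5) = j) × P(Bin(27, p0) ≥ r − j). For p0 = 10% and r = 7 this is 0.125 × 0.0147 + 0.375 × 0.0471 + 0.375 × 0.1266 + 0.125 × 0.2821 = 0.102.

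| Historical CR, cut | None | One retained | Three at 50% |
|---|---|---|---|
| 10%, 7/30 (one-sided 0.05) | 2.6% | 6.4% | 10.2% |
| 20%, 11/30 (one-sided 0.05) | 2.6% | 4.9% | 6.0% |
| 10%, 8/30 (two-sided 0.05) | 0.8% | 2.2% | 4.0% |
| 20%, 12/30 (two-sided 0.05) | 0.9% | 2.0% | 2.5% |

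One retained CR also adds (1 − p0)/30 to the expected rate: 0.9/30 = 3.0 points at p0 = 10%.

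**The case against.** The strongest reply is that the documents imply a workable partition: C is active disease, D is CR with detectable MRD, and CRMRD- stands apart. Protocol 4.1 defines MRD-positive as CR with detection. Protocol 9.3.2 pairs Subgroup D with CRMRD- patients for RFS. ORR, DOR and PFS are confined to C. On that reading only MRD-unknown CR is left over. It should be uncommon, since central MRD testing is planned and a marrow is required within 14 days before dosing. This stands as a sensible inference, but no sentence states it.

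The size is also open to challenge. The first scheduled post-dose disease assessment in Group 2 is Week 12, and other anti-neoplastic therapy is excluded during and after dosing, so a bridging CR would normally have to last about that long to count. The sample size is not power-based, no null rate is fixed, and any formal comparison is left to a separate SAP. This stands too, and the percentages are illustrations only.

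Three stronger readings are tempting but not supported:

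- *That the documents contradict each other on who leaves the primary analysis.* Only the synopsis departs from CRMRD- as a set-aside rule, and that may be a lost subscript. Table 3 and SAP 5.2, 6.4.1.3 and 7.4.5 define secondary summaries and do not take anyone out of the CR rate.
- *That the false-positive chance is 28%.* That is the 10%, 7/30 case with three pre-dose CRs all certain to persist. Nothing in the documents gives that count.
- *That duration of CR may start before first dose.* Its definition does not exclude this, but responders are identified by a best response that opens at first dose, and Protocol 9.3 and SAP 7.1 limit the primary analysis to assessments from the first MT-401 regimen. It merits a minor clarification.

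**Conclusion.** The gap is real and should be fixed. The set-aside rule covers CRMRD- only, subgroup timing is not stated, and best response does not require CR to be absent before dosing. Together these let a bridged MRD-positive or MRD-unknown CR count in Subgroup C if the subgroup is fixed at relapse. If it is reset after bridging, the effect on C is nil for patients with known MRD, and the gap shrinks to MRD-unknown CR.

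The size depends on a count that the documents do not give. One retained patient takes the one-sided chance above 5% at a historical 10% and just under it at 20%. At the SAP's two-sided level one patient stays below the 2.5% tail. More patients, or a lower historical rate, make it matter more. My confidence is medium. Separately, the post-bridging secondary set is plain CR in some sections and CRMRD- in others, which does not sit with the statement in SAP 7.7.

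**What to change.** Before the Group 2 interim:

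1. State that C or D, for analysis, is fixed at the last disease assessment before first dose, and say where MRD-positive CR and MRD-unknown CR go.
2. State that any patient in CR or CRMRD- at that assessment is excluded from the Subgroup C primary CR-rate and duration-of-CR analyses. Report CRMRD- and MRD-unknown CR in the separate post-bridging group, not counted in the 60.
3. Use one definition of the post-bridging set in the Protocol Synopsis, Figure 1 notes, Table 3, 5.1, 9.1.2, 9.3.2 and 9.3.4.1, and in SAP 5.2, 6.4.1.3, 7.4.5 and 7.6.
4. As a minor clarification, say that duration of CR starts at the first response documented after first dose.

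This concerns analysis sets only, not who may be treated. The cost is wording, since the pre-dose marrow is already required. The reported CR rate may be slightly lower, and a few patients may have to be replaced to fill Subgroup C.
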